Study Design:	
This clinical study includes 2 parts:
 
1) Part 1a: An open-label, dose-escalation and regimen-finding to investigate the safety, PK, and PD of SL-901 in patients with advanced solid tumors. In Part 1a, adverse events (AEs) occurring during the first cycle of treatment will be considered for the assessment of dose-limiting toxicities (DLTs), with continued evaluation of AEs in subsequent treatment cycles for further characterization of the safety of SL-901. This part will follow a 3+3 dose-escalation design to determine the MTD of SL-901 when administered on each a QD and BID schedule; single and multiple dose PK assessments will be performed to characterize the exposure of SL-901.2) Part 1b: Up to 4 expansion cohorts of patients with specific genetic alterations that may derive benefit from treatment with a PI3K inhibitor will be treated SL-901 with the dose regimen selected in Part 1a. 
This study will explore different dose levels and schedules of SL-901 given as a single agent, therefore the term “regimen” is comprised of the

unit dose administered and the specified schedule of dosing in a given cohort.

A treatment cycle is 28 days, with daily dosing throughout the cycle.

- In Part 1a, 3 to 6 patients may be enrolled in each regimen to be investigated. Schedules will include QD or BID administrations, as described in [Table 5](#) for each specified dose level.
- In Part 1b, 6 to 12 patients may be enrolled in each expansion cohort (up to 4 expansion cohorts may be opened for enrollment).

Patients may continue to receive SL-901 until disease progression or unacceptable toxicity.

Dose-Escalation Rules:

In Part 1a of the study, AEs occurring during the first cycle of treatment will be considered for the assessment of DLTs, with continued evaluation of AEs in subsequent treatment cycles for further characterization of the safety of SL-901. Further assessment of the safety of SL-901 at the recommended regimen from Part 1a will be performed in Part 1b.

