9.3.5. Efficacy Analyses

- Response evaluation is based upon the Investigator's determination of response using RECIST v1.1 ([Eisenhauer 2009](#)). A response is defined as instance of a patient exhibiting a confirmed complete response (CR) or partial response (PR).

- Objective response rate (ORR) is defined as the number of patients exhibiting response divided by the number of patients qualified for tumor response analysis.
- Progression-free survival (PFS) is defined as the time from the first study drug dose to the first date of objectively determined disease progression or death from any cause. For patients who are still alive at the time of analysis and without evidence of tumor progression, PFS will be censored at the date of the most recent objective progression-free observation. For patients who receive subsequent anticancer therapy before objective disease progression or death, PFS will be censored at the date of the last objective progression-free observation before the date of subsequent therapy.
- Duration of response (DOR) is defined as the time from the date when the measurement criteria are met for CR or PR (whichever status is recorded first) until the date of first observation of objective disease progression. Duration of response will be censored at the date of the last objective progression-free disease assessment for patients who respond to treatment and die without progressive disease (excluding death from study disease). For responding patients not known to have died at the time of the data analysis and who do not have progressive disease, duration of response will be censored at the last progression-free assessment date. The disease control rate (DCR; CR + PR + stable disease) will be similarly analyzed.

For responding patients who receive subsequent anticancer therapy (after discontinuation from all study treatment) before disease progression, duration of response will be censored at the date of last progression-free assessment before the initiation of post-discontinuation anticancer therapy.

- Duration of CR (DOCR) is defined as the time from the date when the measurement criteria are met for CR until the date of first observation of objective disease progression.
- Overall survival (OS) is defined as the time from the first study drug dose to the date of death from any cause. For patients who are still alive at the time of the analysis, OS time will be censored on the date of the patient's last contact.

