11.3. Data imputation

Adverse Events

Completely missing AE dates (i.e., missing day, missing month and missing year) will not be imputed. Partial AE start and stop dates will be imputed according to the rules as follows in a sequential fashion.

In the imputation of missing or partial dates, if the imputed date is after min (death date, cut-off date), min (death date, cut-off date) will be used as the imputed date.

AE Stop Date

- If month and year are present, then impute as the last day of that month
- If only the year is present, impute as December 31 of that year
- If the stop date is entirely missing, assume the event is ongoing

AE Start Date

- If month and year are present, and are not equal to the month and year of the first dose, then imputed as the first day of the month
- If month and year are present, and are equal to the month and year of first dose
 - If stop date is complete and earlier than the date of first dose, then impute as the first day of the month
 - Else impute as the date of first dose
- If only the year is present, and the year is not equal to the year of the first dose, then impute as January 1 of the year
- If only the year is present, and the year is equal to the year of the first dose
 - If stop date is complete and earlier than the date of first dose, then impute as January 1 of the year
 - If stop date is partially missing and the month and year of stop date are earlier than the month and year of first dose, then impute as January 1 of the year
 - Else impute as the date of first dose
- If the start date is entirely missing
 - If the stop date is complete and earlier than the date of first dose, then impute as January 1 of the stop year
 - If the day of stop date is missing, and the month and year are earlier than the month and year of first dose, then impute as January 1 of the stop year
 - If the day and month of stop date are missing, and the year is earlier than the year of first dose, then impute as January 1 of the stop year
 - Else impute as the date of first dose

Prior and Concomitant Medications

The same imputation rules as outlined for the Adverse Events will be used for Prior and Concomitant Medications.

Post-treatment systemic anti-cancer therapy

- In case of partial start date of post-treatment systemic anti-cancer therapy, the date will be imputed as the first day of the month but not earlier than the last dose date.
- In case of completely missing start date, it will be imputed as:

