min [max(PD date + 1, last SL-901 dose date + 1), end date of new anti-cancer therapy].

Last study drug administration

The following rules should be used for the imputation of date of last SL-901 administration:

- If the date of last administration is completely missing and there is no EOT eCRF and no death date, the subject is considered as ongoing and the cut-off date should be used as the last dosing date.
- If the date of last administration is completely or partially missing and the EOT eCRF is available (prior to any death date or withdrawal of consent date, if available):
 - Case 1: The date of last administration is completely missing, and the EOT visit date is complete, then this latter date should be used.
 - Case 2: Only Year(yyyy) of the dose end date is available and yyyy < the year of EOT date:
Use Dec31yyyy
 - Case 3: Only Year(yyyy) of the dose end date is available and yyyy = the year of EOT date:
Use EOT date
 - Case 4: Both Year(yyyy) and Month (mm) are available for the date of last administration, and yyyy = the year of EOT date and mm < the month of EOT visit: Use the last day of the Month (mm).
 - Use min (EOT date, death date) for all other cases.

After imputation, compare the imputed date with the start date of that specific record, if the imputed date is < start date of that record: Use the start date of that record.

Tumor Assessment

Completely or partially missing Tumor Assessment (TA) dates will not be imputed.

- In case date of last TA is missing and there are no previous TA dates, then the date of first study drug admin will be used for censoring

- In case date of last TA is missing and there are previous TA dates, then the previous TA date will be used for censoring
- If there are multiple scan dates associated with an evaluation, the earliest of the scan dates associated with the evaluation will be used as the date of assessment.

Handling of PK concentrations Below the Lower Limit of Quantification and missing sampling timepoints

In all data presentations (except listings), plasma concentration values below the lower limit of quantification (BLQ) will be set to zero before the t_{max} and to “missing” after the t_{max} . Data-replacements will be implemented by the PK analyst from Clinical Pharmacology and Pharmacometrics department.

In listings, BLQ values will be reported as “BLQ”.

A footnote will be added to the listing, tables, and figures, to indicate the lower limit of quantification (LOQ) value.

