11.5.10. Treatment exposure and compliance

The following parameters will be summarized using descriptive statistics:

- Cumulative dose (mg) is the sum of the number of capsules taken at each occasion multiplied by the strength of each capsule.
- Treatment duration from first intake (days) is calculated as (Last dose date – First dose date in run-in period + 1).
- Treatment duration from Cycle 1 Day 1 (days) is calculated as (Last dose date – First dose date in Cycle 1 Day 1 + 1).
- Actual Dose Intensity (mg/day) = [cumulative dose (mg)] / [treatment duration from first intake (days)]
- Planned Dose Intensity (mg/day) = Total daily dose for the cohort (see Table 1).
- Relative Dose Intensity (%) = [actual dose intensity (mg/day)] / [planned dose intensity (mg/day)]

Study treatment administration at the site and study drug accountability as collected in the eCRF, as well as the daily records from the patient diary will be listed.

12. Efficacy evaluations

Efficacy evaluations are based upon the Investigator's assessment.

Tumor assessment will occur at Screening (for identification of baseline disease) and after every 2 cycles of treatment thereafter. Response will be evaluated using Response Evaluation Criteria in Solid Tumors (RECIST) v1.1.

After completion of the EOT visit, patients will then be followed every 90 days for survival status for 12 months. The survival follow-up may be by telephone contact. If the patient discontinued study drug for reasons other than progressive disease, disease assessments should continue to be performed on an every 8-week basis (± 1 week) through 6 months after the first study drug dose and then on an every 90-day basis or until, in the judgment of the Investigator, there is evidence of relapsed or progressive disease.

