12.1.2. Duration of Response

Duration of response (DOR) is defined, for patients with OR, as the time (in months) from the first documentation of objective response (CR or PR) to the date of first documentation of PD.

Duration of Complete Response (DOCR) is defined, for patients with a confirmed BOR of CR, as the time from the first documentation of CR to the date of first documentation of PD.

DOR and DOCR will be calculated as follows:

$$\text{DOR (months)} = [\text{date of event or censoring} - \text{first date of OR} + 1] / 30.4375$$

$$\text{DOCR (months)} = [\text{date of event or censoring} - \text{first date of CR} + 1] / 30.4375$$

DOR and DOCR will be censored at the last tumor assessment if the patient did not have disease progression. If a patient receives a new systemic anti-cancer therapy before disease progression, DOR and DOCR will be censored at the last tumor assessment before the date of initiation of new systemic anti-cancer therapy. In addition, patients who experience PD after ≥ 2 missing tumor assessments will be censored at the last tumor assessments prior to the missed visits.

[figure not shown]
DOR and DOCR will be analyzed by cohort using the Kaplan-Meier method, with the median, 25th and 75th percentiles as well as DOR and DOCR rates at 3, 6 and 12 months (and every 6 months thereafter until the end of follow-up or no more subjects are at risk) reported along with the 2-sided 95% CIs calculated according to Brookmeyer and Crowley using a linear transformation (CONFTYPE=LINEAR in SAS Proc LIFETEST). Number and percentage of patients with event (PD) and censoring reasons will be presented by cohort.

[figure not shown]
DOR and DOCR will be displayed graphically using Kaplan-Meier curves.

These analyses will be presented by cohort both in the Efficacy and in the Per Protocol populations.

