12.1.3. Progression-free survival

Progression-free survival (PFS) is defined as the time (in months) from the date of first intake of SL-901 to the date of the first documentation of PD (per RECIST v1.1) or death due to any cause, whichever occurs first, regardless of whether the patients withdraws from study treatment.

PFS will be analyzed by cohort and overall using the Kaplan-Meier method, with the median, 25th and 75th percentiles as well as PFS rates at 3, 6 and 12 months (and every 6 months thereafter until the end of follow-up or no more subjects are at risk) reported along with the 2-sided 95% CIs calculated according to Brookmeyer and Crowley using a linear transformation (CONFTYPE=LINEAR in SAS Proc LIFETEST). Number and percentage of patients with each event type (PD or death) and censoring reasons will be presented by cohort.

PFS will be displayed graphically using Kaplan-Meier curves.

These analyses will be presented by cohort both in the Efficacy and in the Per Protocol populations.

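### SAP 11.3 imputes a day-missing start of new anti-cancer therapy without regard to progression, so a progression seen earlier in that month can be censored

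*SAP*

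**What the plan says.** SAP 11.3 (Data imputation, post-treatment systemic anti-cancer therapy) has two rules.

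- Partial start date: "the date will be imputed as the first day of the month but not earlier than the last dose date". The only lower bound is the last SL-901 dose.
- Completely missing start date: "min [max(PD date + 1, last SL-901 dose date + 1), end date of new anti-cancer therapy". Here PD date + 1 is also a lower bound, with the therapy end date as a cap.

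The imputed date then decides whether a progression counts.

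- SAP 12.1.2, for new therapy before progression: "DOR and DOCR will be censored at the last tumor assessment before the date of initiation of new systemic anti-cancer therapy".
- Protocol 9.3.5, for therapy before progression or death: "PFS will be censored at the date of the last objective progression-free observation before the date of subsequent therapy". The same section has a matching rule for DOR.
- SAP 12.1.3 (PFS), in its readable text, gives no new-therapy rule. It says only "Number and percentage of patients with each event type (PD or death) and censoring reasons will be presented by cohort".

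SAP section 12 plans scans after the last dose for some patients: "If the patient discontinued study drug for reasons other than progressive disease, disease assessments should continue to be performed on an every 8-week basis". Other patients are dosed up to progression; the Protocol synopsis says "Patients may continue to receive SL-901 until disease progression or unacceptable toxicity".

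**The concern.** The two rules treat progression differently, and the one with more information protects it less. A start date known to the month can be placed before a PD that it followed, whereas a start date not known at all is placed after that PD (unless the therapy is recorded as having ended earlier). Nothing else in SAP 11.3 or 12.1 exempts a PD that falls in the same month as a partly dated therapy.

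Where the therapy truly followed PD, the rule can only take an event away; it cannot add one. The loss occurs in patients who progressed and then switched, so the resulting censoring is informative. DOR, DOCR, PFS and their Kaplan-Meier summaries are reported by cohort, and Part 1a cohorts have 3 to 6 patients per schedule (SAP section 8), so a single event can move a median.

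**Working it through.** The plan gives no figure on this point, so there is none to reproduce. The check applies the rule to dates.

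**Inputs from the documents**
- Current partial-date rule (SAP 11.3): imputed start = max(first of the month, last dose date).
- Completely missing rule (SAP 11.3): min[max(PD + 1, last dose + 1), therapy end].
- Scan interval: 2 cycles of 28 days = 56 days (SAP section 12).
- Month: 30.4375 days (SAP 7.2.1).

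**Assumption:** the gap L from PD to the true therapy start, which the documents do not give. It is varied from 7 to 28 days.

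**1. One patient.** First dose 24 November 2021, 8-week scan 18 January 2022, PD 15 March 2022, new therapy truly started 25 March, recorded as March with no day.

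| Last SL-901 dose | Imputed start, current rule | Before PD? |
|---|---|---|
| 20 February | 1 March | yes, PD lost |
| 8 March | 8 March | yes, PD lost |
| 14 March | 14 March | yes, PD lost |
| 15 March | 15 March | no, PD kept |
| 18 March | 18 March | no, PD kept |

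Had the whole date been missing, the first patient's start would be 16 March and the PD would count, provided the therapy had not ended before then.

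With the inclusive day count that SAP 12.1.2 and 12.1.4 use, PFS is an event at 112/30.4375 = 3.68 months. After the imputation and the Protocol 9.3.5 rule, it is censored at 56/30.4375 = 1.84 months if the 8-week scan is the last one before the imputed start.

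**2. Share of PDs lost.** This is conditional on a missing day and a last dose at least one day before PD. A PD is lost when PD and PD + L fall in the same month and PD is not on the 1st. In a month of m days that covers PD days 2 to m − L, which is m − L − 1 days (zero if negative). With PD dates spread evenly over 365 days:

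| L (days) | PD days lost per year | Share |
|---|---|---|
| 7 | 365 − 12×8 = 269 | 0.737 |
| 14 | 365 − 12×15 = 185 | 0.507 |
| 21 | 365 − 12×22 = 101 | 0.277 |
| 28 | 7×2 + 4×1 + 0 = 18 | 0.049 |

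Enumerating every PD date over two calendar years gave the same shares for last doses 1 to 56 days before PD, and zero when the last dose was on or after PD.

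**3. Effect on a cohort of three** (illustrative times).
- PDs at 1.84, 3.68 and 5.52 months: S = 0.667, 0.333, 0; median 3.68. With the middle PD censored at 1.84: S = 0.667 at 1.84 and 0 at 5.52; median 5.52. The median rises.
- PDs at 7, 8 and 9 months: S = 0.667, 0.333, 0; median 8. With the last PD censored at 6, only two patients are at risk at 7 months: S(7) = 0.5 and S(8) = 0; median 7 (7.5 if the midpoint is taken). The median falls.

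**The case against.** The strongest reply is that the exposed group is narrow. The error needs a missing day, a last dose strictly before PD, and PD and therapy start in the same month with PD not on the 1st. DOR also needs a confirmed responder. Patients dosed up to PD, or beyond it as Protocol 7.3 allows, are fully protected by the last-dose bound. Sites are queried about missing data (Protocol 10.1.7), and individual DOR and PFS listings are planned (SAP 13.2.2), so an odd censoring could be noticed. All of this stands and limits the size. It does not remove the fault: scans after early discontinuation are planned, and a listing does not correct the tables and curves.

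A second reply is that bounding by PD can err the other way. After discontinuation, scans are 8 weeks and later 90 days apart, so a therapy could truly have begun before the scan in that month. This is a fair trade-off and calls for showing both results. The SAP already accepts the same error where the whole date is missing.

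A reader might infer three stronger points that the documents do not support.
- That PFS and DOR are always inflated. Censoring also removes a patient from later risk sets, and the second cohort above moves down.
- That the SAP itself produces the PFS error. That link rests on Protocol 9.3.5; a censoring table for SAP 12.1.3 may be absent from the readable text.
- That losing the month as well as the day would trigger the PD bound. That bound applies only to a completely missing date, which SAP 11.3 spells out for adverse events as day, month and year. A year-only start is still partial, and the first-of-month rule gives no result for it.

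**Conclusion.** The point holds, as a minor one. The partial-date rule in SAP 11.3 can turn an observed progression into a censored observation when the last dose precedes PD and a later, day-missing therapy start shares its month. For DOR and DOCR this follows from the SAP alone; for PFS it follows from the SAP imputation combined with Protocol 9.3.5.

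The shares of about 74%, 51%, 28% and 5% rest on assumed gaps of 7, 14, 21 and 28 days and an even spread of PD dates. They apply only within the exposed group and are not a loss rate for the trial; the number of such patients is not given and may be small or zero. The effect on a cohort's Kaplan-Meier median is often upward but depends on the other patients' times.

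The endpoints concerned are secondary and descriptive, Part 1b was not started, and the MTD and safety conclusions do not depend on them.

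**What to change.** In SAP 11.3, impute a start date with known month and missing day as the latest of:
- the first day of the known month;
- last SL-901 dose date + 1;
- PD date + 1, when PD falls in that month.

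Cap the result at the end of the month and at the therapy end date. Report DOR, DOCR and PFS under the current rule as a sensitivity analysis.

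Check: in the March example the three lost PDs now get an imputed start of 16 March and stay events. In general, if therapy followed PD in the same month, PD + 1 is no later than month end and no later than the therapy end date, so the imputed start is after PD. If therapy began in a later month, the first of that month is already after PD. No PD is lost when therapy truly followed it.

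The cost is one sentence in the SAP, one line of code and a repeat of the affected tables; no new data are needed. The downside is that a therapy truly started before PD in the same month would count as starting after it, unless its recorded end date shows otherwise. The sensitivity analysis shows how much that matters. The SAP is to be finalised before database lock (SAP section 3); if that has passed, Protocol 9.4 provides for documenting the change in the clinical study report.

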- 16) Known hypersensitivity or allergy to the active ingredient or excipients of SL-901.
- 17) Breast-feeding females.

[figure not shown]
Test Products, Doses, and Mode of Administration:	In Part 1a, the SL-901 starting dose on the 20 mg on both the QD and BID schedule. Dose levels planned to be tested in both QD and BID schedules will be tested in parallel, with enrollment to the current cohort for each schedule conducted on an every other patient basis (see Table 5). A treatment cycle is 28 days, with daily dosing throughout the cycle. The regimen of SL-901 for Part 1b of the study will be based on the clinical experience from Part 1a.
Duration of Treatment:	Patients whose disease has not progressed and who have not discontinued due to toxicity, may continue to receive additional cycles of SL-901 at the same dose and schedule.

[figure not shown]

[figure not shown]
Safety:	
Patients' medical history will be collected during Screening and updated prior to the first SL-901 dose. Safety assessments include physical examinations, safety laboratories (clinical chemistry, hematology, and coagulation), vital signs and weight, ECOG performance status, and electrocardiograms (ECGs) (performed according to the schedule in Table 8). Assessment of AEs and concomitant medications will be performed for each patient throughout the study.
 
An End-of-Treatment (EOT) visit to include safety laboratory evaluation plus adverse events and concomitant medication checks, will be conducted 30 days after the last dose of SL-901.

Efficacy:	
Tumor assessment by will occur at Screening (for identification of baseline disease) and after every 2 cycles of treatment thereafter. Response will be evaluated using Response Evaluation Criteria in Solid Tumors (RECIST) v1.1 (Eisenhauer 2009).
 
After completion of the EOT visit, patients will then be followed every 90 days for survival status for 12 months. The survival follow-up may be by telephone contact. If the patient discontinued study drug for reasons other than progressive disease, disease assessments should continue to be performed on an every 8-week basis (± 1 week) through 6 months after the first study drug dose and then on an every 90-day basis or until, in the judgment of the Investigator, there is evidence of relapsed or progressive disease.

Statistical Methods:	Study data will be reviewed in accordance with the Statistical Analysis Plan described in Section 9.3 .

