7.3. Treatment Discontinuation

Study drug may be discontinued for any of the following reasons:

- Progression of disease that, in the opinion of the Investigator, precludes further study treatment. After consultation with the Sponsor, SL-901 may be continued for a patient who has met the criteria for progressive disease but in the Investigator's opinion, continues to derive benefit from study treatment.
- Occurrence of an unacceptable AE, including DLT.
- Pregnancy.
- SL-901 interruption due to study drug-related toxicity for >1 cycle (i.e., >28 days). Interruptions or delays >28 days for reasons other than AEs and/or in the setting of sustained disease control may be acceptable and are to be discussed with the Medical Monitor.
- Patient requires use of a prohibited concomitant medication or therapy.
- General or specific changes in the patient's condition unacceptable for further treatment within the study parameters, in the judgment of the Investigator.
- Non-compliance.

- Lost to follow-up.
- Patient withdrawal of consent.
- Sponsor request.
- Other.

All study procedures outlined for the End-of-Treatment (EOT) visit should be performed 30 days (± 3 days) after the last study drug dose.

In Part 1a, patients who receive <75% of the planned SL-901 doses in C1 and/or discontinue from the study before completing study assessments through C2D1 for reasons other than DLT are to be replaced.

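### When the last-dose date is missing, the SAP substitutes the EOT visit date, which the protocol sets about 30 days after the last dose, so that patient's treatment duration is overstated by 27 to 33 days

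*SAP*

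**What the plan says.** **Timing of the EOT visit.** Protocol 7.3: "All study procedures outlined for the End-of-Treatment (EOT) visit should be performed 30 days (± 3 days) after the last study drug dose". The safety paragraph of the synopsis agrees: the visit "will be conducted 30 days after the last dose of SL-901".

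**Imputation of last dose.** SAP 11.3, under last study drug administration, covers patients with an EOT form and a missing or partial last-dose date.
- Case 1: "The date of last administration is completely missing, and the EOT visit date is complete, then this latter date should be used".
- Case 3 also uses the EOT date. Its condition is "Only Year(yyyy) of the dose end date is available and yyyy = the year of EOT date".
- Case 2 (year known and before the EOT year) uses 31 December.
- Case 4 (month known, same year as EOT, earlier month) uses the last day of that month.
- The remainder: "Use min (EOT date, death date) for all other cases".

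The one check after imputation compares the result with the start date of the dosing record. It moves a date that is too early and leaves one that is too late.

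**Where the date is used.** SAP 11.5.10: "Treatment duration from first intake (days) is calculated as (Last dose date", minus the first run-in dose date, plus one. Actual dose intensity is cumulative dose over that duration, and relative dose intensity divides the result by the cohort's total daily dose. Last dose also closes the TEAE window (SAP 7.2.2) and enters the imputed start of later anti-cancer therapy. For a partial start date, "the date will be imputed as the first day of the month but not earlier than the last dose date"; for a completely missing one, last dose plus one day enters the formula. The therapy start in turn determines DOR and DOCR censoring (SAP 12.1.2).

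**The concern.** The rule treats the EOT visit as the end of dosing. In this protocol it is a follow-up visit about a month later, so the substituted date is late by design for anyone who attends on schedule.

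The error in last dose and duration has one direction. Nothing in the formula offsets it, because the numerator of dose intensity is built from capsules taken and does not use the imputed date. The affected patient appears to have been treated for longer and at lower intensity than was the case. Exposure is part of the safety evaluation (SAP 11.5), and safety is a primary objective. With 3 to 6 patients per cohort, one such patient is visible in a cohort summary.

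**Working it through.** The documents give no figure for this error, so there is none to reproduce. The check is date arithmetic.

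**Inputs**
- EOT lag L = 30 days, range 27 to 33 (protocol 7.3).
- Run-in dose 3 to 7 days before C1D1 (protocol Table 8). The main example assumes g = 5.
- Cycle length 28 days, daily dosing (protocol 4.1.1).
- Duration and dose-intensity formulas (SAP 11.5.10).
- Assumptions: QD schedule, one run-in dose, every dose taken, all capsule counts known, EOT held on schedule.

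**Formulas for c full cycles**
- True duration D = g + 28c
- Doses taken N = 1 + 28c
- Imputed duration under Case 1 = D + L
- Relative dose intensity: true N/D, imputed N/(D + L)

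**Results with g = 5, L = 30**

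| Cycles | N | True duration | Imputed duration | True RDI | Imputed RDI |
|---|---|---|---|---|---|
| 1 | 29 | 5 + 28 = 33 | 63 (+91%) | 29/33 = 88% | 29/63 = 46% |
| 6 | 169 | 5 + 168 = 173 | 203 (+17%) | 169/173 = 98% | 169/203 = 83% |

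**Sensitivity to the run-in gap (3 to 7 days), L = 30**
- 1 cycle: 31–35 days become 61–65; RDI 82.9–93.5% becomes 44.6–47.5%.
- 2 cycles: 59–63 become 89–93; RDI 90.5–96.6% becomes 61.3–64.0%.
- 4 cycles: 115–119 become 145–149.
- 6 cycles: 171–175 become 201–205.

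**Cohort mean.** One affected patient moves mean duration by 30/6 = 5 to 30/3 = 10 days.

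**Partial dates**
- Last dose recorded as December, EOT on 10 January: Case 4 needs the same year, so it does not apply. The fallback, absent an earlier death, assigns 10 January, which is outside the recorded month and year. EOT minus 30 days would be 11 December.
- Last dose recorded as March (true date 10 March), EOT on 9 April: Case 4 gives 31 March, 21 days late and only 9 days before EOT.

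**TEAE window.** It nominally ends 57 to 63 days after the true last dose (27 + 30 to 33 + 30) instead of 30.

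**The case against.** Most of the case on the other side concerns reach, and most of it stands.

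- **Few patients may be affected.** Dispensing and returns are logged (protocol 6.3), missing data are queried (protocol 10.1.7), and diary and administration records are listed (SAP 11.5.10). A reader might infer that exposure in the trial as a whole is overstated by a month. The documents do not support that: the error applies per affected patient, and no count is given.
- **The example assumes that intakes are known but the last date is not.** If capsule counts are missing too, cumulative dose is uncertain and 46% does not follow. One cycle is also the most extreme case shown.
- **TEAEs.** A reader might infer that TEAE counts are inflated. AEs are recorded only through 30 days after last dose (protocol 8.2.2), so the longer window can reclassify only later events that were entered anyway.
- **DOR and DOCR.** A reader might infer that response durations are biased upward. That needs a responder without prior PD, a missing last-dose date, a missing or partial new-therapy date, and a scan inside the shifted interval. Nor is the direction fixed. Last dose plus one is the earliest day on which post-treatment therapy could start, so if therapy began more than a month later, the EOT-based date is closer to the truth.
- **EOT might mean the day treatment stopped.** This does not stand. Case 1 refers to the EOT visit, SAP 11.4 names the treatment-discontinuation form separately, and the SAP text does not redefine the visit. One caveat is that the SAP cites protocol v2.0 and subsequent amendments, and its flow chart is not shown; the timing here comes from protocol v3.0.
- **Subtracting 30 days everywhere would create new errors.** This is correct. If the recorded last-dose month equals the EOT month, the result usually falls in the previous month. If only the year is known and EOT is on 1 to 30 January, it falls in the previous year. An incomplete EOT date allows no subtraction.

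**Conclusion.** Case 1 conflicts with the protocol's visit schedule and is wrong as written. For a patient with a completely missing last-dose date and an on-schedule EOT visit, last dose is placed 27 to 33 days late, duration is overstated by the same amount, and dose intensity is understated. Case 3 and the fallback can err in the same direction for partial dates, though by an amount that depends on what was recorded.

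The direct consequence is for the treatment exposure summary (Table 14.1.3.9), which is descriptive. The DLT and MTD rules, overall survival and PK concentrations do not use the imputed date, and Part 1b was not started. The percentages above depend on the stated adherence, run-in and capsule-count assumptions; the 27-to-33-day figure depends only on the visit being held in its window. The effect on cohort summaries cannot be sized without the number of missing dates. The correction is worth making because it is simple and the error is systematic for those it touches.

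**What to change.** Replace the last-dose imputation in SAP 11.3 with the following order.

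1. Use the last dosing date in the patient diary or site administration record, where there is one.
2. Otherwise, if the EOT date is complete, use EOT minus 30 days. The result must not fall before the last documented dose, nor after death or cut-off. It must stay inside any recorded month or year; if it falls outside, move it to the nearest day within that period. This replaces Case 1, Case 3 and the fallback.
3. In Cases 2 and 4, cap the end-of-year or end-of-month value at EOT minus 27 days, subject to the same bounds. In the March example, the cap gives 13 March instead of 31 March.
4. If the EOT date is incomplete, use the last documented dose.

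For a completely missing date with an on-schedule visit, step 2 reduces the error from between +27 and +33 days to within ±3 days. In the output, flag imputed dates in the exposure listing and report how many there are per cohort, so that readers can judge the effect.

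The cost is a few lines of SAP text and one derivation in the exposure dataset, preferably before database lock. The records needed for step 1 are already collected. No clinical rule changes.
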